9.0 Criteria for Removal from the Study

Reason to take patients off study include (but are not limited to) the following:

- Progressive disease
- Patient refusal
- Patient non-compliance
- Physician judgment
- Pattern of patient non-compliance

10.0 Data Monitoring Plan

This is a single arm phase II study in patients with MDS who have failed therapy with or are intolerant of hypomethylating agents.

Primary objective: complete response (CR); overall survival.

Secondary objective: duration of response; relapse-free survival; safety.

It will be postulated that the treatment can achieve a CR rate of 20% and a median overall survival time of 6 months.

A maximum of 80 patient will be accrued at a rate of 2 to 5 patients per month (maximum accrual period 3.33 yrs). The CR, overall survival and toxicity will be monitored during the study, and all data will be used to update the prior distributions for toxicity and efficacy parameters. The study will be stopped for toxicity and futility based on the following stopping rules.

Efficacy monitoring

Complete response and overall survival will be monitored separately. The method of Thall, Simon, and Estey [9] will be used to monitor response and Bayesian time-to-event model [10] will be used to monitor overall survival.

a. CR

CR will be monitored in all pts using the method of Thall et al.[9] Denote the probability of CR by PE. We assume $PE \sim \text{beta}(0.4, 1.6)$. We will stop the trial if at any point that there is < 1% chance that the CR rate is > 20%. Stopping boundaries corresponding to this stopping rule and operating characteristics are listed in tables 1a and 1b. CR in the 4 months after the treatment will be included in the primary analysis.

Table 1a. Stop accrual if the number of response is equal to or less than indicated (i.e., # response) among number of patients accrued (i.e., # Patients). (PL=0.01)

# CR	0	1	2	3	4	5	6	7	8
# Pts	15	24	33	41	49	56	64	71	78

Table 1b: Operating characteristics of response (based on 10000 simulations) (PL=0.01)

True Probability	Stop Probability	Trial Sample Size Percentile		
		25%	50%	75%
0.05	0.992	15	24	33
0.1	0.735	24	41	80
0.15	0.301	64	80	80
0.2	0.086	80	80	80

b. Overall survival

Bayesian time-to-event model will be used to monitor the overall survival [10]. Let T_e and T_s represent the overall survival time for the study and the historical treatment, respectively. We assume $T_e|Me$ and $T_s|Ms$ follow an exponential distribution with median Me and Ms , respectively. We further assume that the prior for Ms follows Inverse Gamma (IG) (35, 204) to reflect our knowledge of overall survival from the historical data, which has a mean of 6 months and a variance of 1.09. The prior for Me is assumed to be IG (3,12), which has the same mean as Ms but with a much larger variance (36) to reflect much greater uncertainty about the median time to progression of the study treatment.

The study will be monitored after the first 14 pts have been enrolled and then be repeated every month. The study will be stopped early if, based on the available data, we have little reason to believe that the median OS is 6 months or more. Formally, we'll stop the study early if there is < 5% chance that the median OS is 6 months or more. The operating characteristics of this decision rule are shown in the following table:

Table 2: Operating characteristics of Efficacy Monitoring(PL=0.05)

True Median OS (Mos)	P(Stop)	Mean Number of Pts (25%, 75%)
2	1	18 (15,20)
4	0.835	42 (21,63)
6	0.079	76 (80,80)
7	0.024	79 (80,80)

Toxicity Monitoring

Toxicity will be monitored in all pts using the method of Thall et al 1995 [9]. Toxicity is defined as non-hematologic grade 3 or 4 toxicities during the treatment course. Denote the probability of toxicity by E, where study drug related toxicity is defined as any Grade 3 or greater non-hematological toxicities. We assume $E \sim \text{beta}(0.6, 1.4)$. We will stop the trail if at any point $\Pr(E > 0.30 | \text{data}) > 0.95$, i.e. if at any time during the study, we determine that there is > 95% chance that the study drug related toxicity rate is > 30%. Toxicity monitoring will be done in cohorts and the trial will be stopped if (number of toxicity observed / among number of patients) $\geq 6/10, 8/15, 10/20, 12/25, 14/30, 16/35, 18/40, 19/45, 21/50, 23/55, 25/60, 26/65, 28/70, 30/75, \text{ and } 31/80$.

Table 3: The operating characteristics for toxicity monitoring are summarized in the following table

True toxicity probability	Probability of early stop	Sample size percentiles (10, 25, 50, 75, 90)
0.1	0	80 80 80 80 80
0.2	0.012	80 80 80 80 80
0.3	0.188	23 80 80 80 80
0.4	0.755	10 15 36 79 80
0.5	0.99	10 10 15 25 41

Early termination of the study can be caused by either lack of efficacy or too much toxicity. If the efficacy and toxicity are considered jointly, the stopping probabilities will be higher than the probabilities shown in Tables 1 to 3.

Table 4 shows several scenarios of the joint stopping probabilities assuming that efficacy and toxicity are independent.

Table 4: Operating characteristics considering efficacy and toxicity jointly

True probability of CR	True Median OS (mos)	True Probability of Toxicity	Early Stop Probability
0.25	7	0.2	0.06
0.25	4	0.2	0.84
0.25	7	0.5	0.99
0.2	6	0.3	0.316
0.1	4	0.4	0.989
0.1	6	0.2	0.759
0.1	7	0.4	0.937

All calculations were performed using OnearmTTE and Multc99.

Trial Conduct

The Department of Biostatistics will provide and maintain a website ("Clinical Trial Conduct") for monitoring of the overall survival. The Clinical Trial Conduct website resides on a secure server, and access is gained through usernames and passwords provided to personnel responsible for enrolling patients and updating patient data. The website is accessed through a browser using secure socket layer (SSL) technology.

Personnel responsible for enrolling patients on trials will be trained in the use of the trial website, with emphasis on the importance of timely updating of follow-up times and recording of events. The monitoring rules for the overall survival will be automatically evaluated each time patient data are updated on the trial website. If the stopping rule is met, the study statistician, research nurse, and principal investigator will each receive an email notification that the stopping boundary has been met.

Analysis Plan

For discrete or categorical data, descriptive statistics will include tabulations of frequencies. For continuous data, summary statistics including n, mean, standard deviation, median, minimum and maximum will be computed. The posterior CR rate and its 95% credible intervals will be estimated. The Kaplan-Meier method will be used to estimate the probability of the overall survival.

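### The written CR futility rule first stops the trial at 0 responses in 13 patients, but Table 1a starts at 0 in 15, and Table 1b describes the table's rule rather than the written one

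*Combined protocol and SAP*

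**What the plan says.** All of this is in section 10.0, Data Monitoring Plan, under Efficacy monitoring.

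- **Prior.** The CR probability has a beta(0.4, 1.6) prior, with mean 0.4/2.0 = 0.20.
- **Rule.** "We will stop the trial if at any point that there is < 1% chance that the CR rate is > 20" per cent.
- **Who is monitored.** "CR will be monitored in all pts using the method of Thall et al.[9"]. No minimum number of patients and no cohort size is given for CR.
- **Link to the tables.** "Stopping boundaries corresponding to this stopping rule and operating characteristics are listed in tables 1a and 1b".
- **Table 1a.** For 0 to 8 CRs the patient numbers are "Pts 15 24 33 41 49 56 64 71 78", so the first boundary is 0 CRs in 15 patients.
- **Table 1b.** The stop probabilities are 0.992, 0.735, 0.301 and 0.086 at true CR rates of 0.05, 0.10, 0.15 and 0.20, from 10,000 simulations, with a maximum of 80 patients.

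The other two monitoring rules in the same section do state when looking begins. Overall survival is first examined after 14 patients, and toxicity is examined in cohorts with a first boundary at 10 patients.

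**The concern.** The text defines the rule by a posterior probability that can be checked after every patient, and it presents Table 1a as the consequence of that rule. If the first entry does not follow from the rule, the trial team has two instructions that disagree when 13 or 14 patients have been evaluated with no CR.

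That is where a conflict is most likely if the regimen is not working. The chance of no CR in the first 13 patients is 0.95^13 = 51% at a true rate of 5% and 0.90^13 = 25% at 10%. It is 0.80^13 = 5.5% at the postulated 20%. The error rates in Tables 1b and 4 can also describe only one of the two rules.

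**Working it through.** **Inputs**, all from section 10.0: prior beta(0.4, 1.6); standard 20%; cut-off 1%; maximum 80 patients; a look after each patient, as the wording implies.

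**Posterior.** After r CRs in n patients the posterior is beta(0.4 + r, 1.6 + n − r), and

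Pr(CR rate > 0.20 | r, n) = 1 − F(0.20; 0.4 + r, 1.6 + n − r).

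**Step 1: reproduce the eight later entries.** For each r, find the first n at which this falls below 0.01.

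| r | Table 1a n | Posterior at n | Posterior at n − 1 |
|---|---|---|---|
| 1 | 24 | 0.0094 | 0.0116 |
| 2 | 33 | 0.0095 | 0.0114 |
| 3 | 41 | 0.0098 | 0.0116 |
| 4 | 49 | 0.0094 | 0.0110 |
| 5 | 56 | 0.0100 (0.00998) | 0.0116 |
| 6 | 64 | 0.0089 | 0.0102 |
| 7 | 71 | 0.0089 | 0.0102 |
| 8 | 78 | 0.0088 | 0.0100 (0.01005) |

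All eight are exactly the first n that meets the rule. This confirms the prior, the fixed 20% standard, the cut-off and the patient-by-patient look.

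**Step 2: the first entry (r = 0).**

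| n | 12 | 13 | 14 | 15 |
|---|---|---|---|---|
| Pr(CR rate > 20%) | 0.0104 | 0.0080 | 0.0062 | 0.0048 |

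The rule is first met at 0/13, not 0/15.

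**Step 3: which rule Table 1b describes.** Exact binomial forward recursion to n = 80, removing stopped paths at each boundary:

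| True CR rate | Printed | First boundary 0/15 | First boundary 0/13 |
|---|---|---|---|
| 0.05 | 0.992 | 0.991 | 0.991 |
| 0.10 | 0.735 | 0.739 | 0.747 |
| 0.15 | 0.301 | 0.303 | 0.320 |
| 0.20 | 0.086 | 0.086 | 0.102 |

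The simulation standard error is √(p(1 − p)/10,000). At a true rate of 0.20 under the written rule it is √(0.1019 × 0.8981/10,000) = 0.0030, so the printed value is about 5 standard errors away. At 0.15 it is about 4 away. Against the 0/15 boundary no row differs by more than 1.3 standard errors.

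The sample-size percentiles agree with this. Table 1b prints 15/24/33 at a true rate of 0.05. The 0/15 boundary gives 15/24/33 and the written rule gives 13/13/33. At 0.10 the 25th percentile is 24 as printed and 13 under the written rule. One printed percentile, 64 at 0.15, comes out as 56 by exact calculation. It is borderline (cumulative stopping 0.2508 at n = 56) and within simulation noise.

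**Step 4: Table 4.** Under the stated independence, joint stopping = 1 − (1 − CR)(1 − OS)(1 − toxicity). For the row with CR 0.2, OS 6 months and toxicity 0.3:

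- Table 1a boundary: 1 − 0.914 × 0.921 × 0.812 = 0.316, as printed.
- Written rule: 1 − 0.898 × 0.921 × 0.812 = 0.328.

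The row (0.1, 6, 0.2) moves from 0.759 to about 0.770, and (0.25, 7, 0.2) from 0.06 to about 0.07. The other four rows move by about 0.003 or less.

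**Step 5: other explanations tried.** No other prior, cut-off or random historical standard that was tried gives 0/15 together with the other eight entries. Borrowing the 14-patient start of the survival rule gives 0/14 and a stop probability of 0.093 at a true rate of 20%, which does not match either. An unstated 15-patient minimum before the first CR look gives all of Table 1a and, within simulation error, all of Table 1b.

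**The case against.** The arithmetic is not in dispute. The case on the other side is that the effect is small and the intention can be guessed.

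- **Effect on the design.** Only two states conflict, 0/13 and 0/14. By exact calculation, stop probabilities move by at most about 0.017. Mean sample size moves by 2 patients at most: 26.0 against 24.2 at a true rate of 5%, 47.6 against 45.7 at 10%, 75.7 against 74.5 at 20%. The large percentile shifts (a median of 24 against 13 at 5%) arise because 46% and 51% fall on either side of one half; they do not mean that the trial halves. This stands.
- **Timing.** At 2 to 5 patients per month, two patients is 0.4 to 1 month of accrual. With CR counted over four months, 8 to 20 further patients could enrol in one response window. This stands, and it limits the practical consequence.
- **The table is the operating instruction.** Table 1a tells the team when to stop accrual, and Tables 1b and 4 agree with it. The toxicity rule uses the same any-point wording and then monitors in cohorts. This makes a 15-patient first look a plausible reading. However, the toxicity text states its cohorts and the CR text states no first look. The automated website check is described only for overall survival, so nothing in the plan settles which CR instruction governs.

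**Conclusion.** The concern holds. As written, the CR rule first stops at 0/13. Table 1a, which is said to correspond to it, first stops at 0/15. Tables 1b and 4 give the operating characteristics of the 0/15 version. At the postulated CR rate of 20%, the chance of stopping on the CR rule is 0.102 under the text and 0.086 under the table.

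This rests on the stated prior, the fixed 20% standard, a look after every patient and, for the Table 4 figures, independence. The eight matching entries support the first three. That the cause is an undocumented 15-patient minimum is an inference, although it fits the printed figures. No design conclusion is overturned. The point deserves correction because it is a trial-level threshold for a primary endpoint and the correction costs almost nothing.

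**What to change.** Choose one rule and make the text and tables agree.

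1. **If a 15-patient minimum was intended:** add one sentence to the CR rule saying that the first evaluation takes place at 15 patients and that evaluation continues after each patient from then on. Tables 1a, 1b and 4 stay as printed.
2. **If monitoring from the first patient was intended:** change the first boundary in Table 1a to 0/13 and rerun Tables 1b and 4. Expected stop probabilities are about 0.991, 0.747, 0.320 and 0.102 at true rates of 0.05, 0.10, 0.15 and 0.20, with sample-size percentiles of 13/13/33, 13/41/80, 56/80/80 and 80/80/80.

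The first option costs a sentence. The second costs one table cell and a short rerun. Neither adds patients.

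### Table 1a applies the CR futility boundary to patients accrued; read literally, it counts pending patients as non-responders and stops a 20% CR regimen more often than the stated 0.086

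*Combined protocol and SAP*

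**What the plan says.** All of this is in section 10.0, Data Monitoring Plan, unless noted.

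- The rule: "We will stop the trial if at any point that there is < 1% chance that the CR rate is > 20" per cent, with a beta(0.4, 1.6) prior on the CR rate.
- The link to the tables: "Stopping boundaries corresponding to this stopping rule and operating characteristics are listed in tables 1a and 1b".
- The Table 1a caption: "Stop accrual if the number of response is equal to or less than indicated (i.e., # response) among number of patients accrued". The boundaries are 0/15, 1/24, 2/33, 3/41, 4/49, 5/56, 6/64, 7/71 and 8/78.
- The population: "CR will be monitored in all pts".
- The window: "CR in the 4 months after the treatment will be included in the primary analysis". The start of this window is not defined further.
- Accrual: up to 80 patients, "accrued at a rate of 2 to 5 patients per month".
- Trial Conduct: "The monitoring rules for the overall survival will be automatically evaluated each time patient data are updated on the trial website". Nothing equivalent is written for CR.

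Section 7.0 puts the first marrow at day 28, plus or minus 7 days. Section 8.0 requires a response to last at least 4 weeks. Section 5.1.1 allows up to three induction cycles, 4 to 8 weeks apart. No section restricts the CR denominator to patients with a known outcome, pauses accrual while outcomes mature, or says how pending patients are counted.

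**The concern.** A posterior for the CR rate is updated with observed outcomes. Patients accrued is a different quantity, because the most recent enrolees cannot yet have a documented CR. They enlarge the denominator and cannot add to the numerator, so the caption and the rule it is said to implement can give opposite decisions on the same data.

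CR is one of two primary endpoints, and 20% is the rate the trial postulates. If the caption is followed as worded, a regimen that meets this target is stopped for futility more often than Table 1b reports. Table 4 is built from the same CR stop probabilities and would be understated wherever CR stopping carries weight.

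**Working it through.** **Step 1: reproduce Table 1a.** With r CRs among n known outcomes, the posterior is beta(0.4 + r, 1.6 + n − r). The rule stops when Pr(CR rate > 0.20) < 1%.

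| CRs | Table 1a n | Posterior, all n known | Posterior, n − 1 known |
|---|---|---|---|
| 1 | 24 | 0.94% | 1.16% |
| 2 | 33 | 0.95% | 1.14% |
| 3 | 41 | 0.98% | 1.16% |
| 4 | 49 | 0.94% | 1.10% |
| 5 | 56 | 0.998% | 1.16% |
| 6 | 64 | 0.89% | 1.02% |
| 7 | 71 | 0.89% | 1.02% |
| 8 | 78 | 0.88% | 1.005% |

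For 1 to 8 CRs, the tabled n is the smallest that meets the rule with every outcome known. With one outcome pending, the rule says continue and Table 1a says stop. The 0-CR entry has slack. The rule is first met at n = 13 (0.80%; at 12 it is 1.04%), while the table uses 15. There the two instructions conflict only with three or more pending, for example 1.75% with 10 known and 6.9% with 5 known.

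**Step 2: reproduce Table 1b.** Let f(n, r) be the probability of being unstopped with r CRs after n outcomes. Then f(n, r) = (1 − p) f(n − 1, r) + p f(n − 1, r − 1). From n = 15 to 80, mass at or below the Table 1a limit is moved to stopped. With instant outcomes this gives:

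| True CR | 0.05 | 0.10 | 0.15 | 0.20 |
|---|---|---|---|---|
| Recomputed | 0.991 | 0.739 | 0.303 | 0.086 |
| Table 1b | 0.992 | 0.735 | 0.301 | 0.086 |

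Table 1b therefore describes a trial in which each CR is known at enrolment.

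**Step 3: apply the caption literally.** Use the same recursion, but compare CRs among the first n − m patients with the limit at n accrued. This needs no time-to-CR assumption. At true CR 20%:

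| Pending, m | 0 | 1 | 2 | 3 | 5 | 10 |
|---|---|---|---|---|---|---|
| P(stop) | 0.086 | 0.102 | 0.119 | 0.140 | 0.194 | 0.439 |

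**Step 4: how many would be pending?** The documents give no time-to-CR distribution or CR look schedule, so a range is needed.

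Most favourable case: CR declared at day 21 without waiting for the 4-week duration, even accrual, and a look just before the next enrolment. Taking 30.44 days per month, enrolments are 15.2, 8.7 or 6.1 days apart at 2, 3.5 or 5 per month. That leaves 1, 2 or 3 patients under 21 days, so P(stop) is 0.102, 0.119 or 0.140.

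Later cases, with a look at each enrolment (simulated, 20,000 trials per cell; even to Poisson accrual):

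| CR known at | 2/month | 3.5/month | 5/month |
|---|---|---|---|
| Day 21 | 0.12–0.13 | 0.14–0.16 | 0.17–0.20 |
| Day 28 plus 4 weeks | 0.16–0.21 | 0.27–0.34 | 0.44–0.53 |
| Uniform over months 1–4 | 0.22–0.26 | 0.40–0.47 | 0.65–0.69 |

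Crossings are treated as final, since no reopening is written.

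**Step 5: Table 4.** Table 4 assumes efficacy and toxicity are independent. For CR 0.2, OS 6 months, toxicity 0.3: 1 − (1 − 0.086)(1 − 0.079)(1 − 0.188) = 0.316, as stated. Replacing 0.086 by 0.102 gives 1 − 0.898 × 0.921 × 0.812 = 0.328. With 0.194 it is 1 − 0.806 × 0.921 × 0.812 = 0.397.

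**The case against.** The strongest reply is that the posterior rule governs. It is correctly specified, Table 1a is said to correspond to it, and section 10.0 also says that the accumulating data will update the priors. A statistician could simply count known outcomes, in which case the tabled boundaries are right and the fault is one word in a caption. This stands in part. It rules out saying that the CR rule itself or the boundary numbers are wrong. It does not remove the conflict, because nothing in the plan tells the user to depart from the caption.

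A reader might infer that Table 1a is the only form in which the CR rule would be run, because the website evaluation is described for overall survival only. The documents do not support that. They are silent on how CR monitoring is carried out, and silence does not show that staff would score pending patients as failures.

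A reader might also take the upper figures as the expected error rate. They are not. They need 5 patients per month throughout, late and spread-out CR times, and irreversible stopping. In the simulated settings, 37–94% of crossings would lie above the boundary once patients already enrolled resolved, so a reversible hold would undo part of the excess. At the other end, 0.102 against 0.086 is a small gap.

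Nor do the two instructions always conflict. At 0 CR in 15 accrued, with day-21 marrows, 3.5 patients per month and a look just before the next enrolment, 13 outcomes are known. The posterior is 0.80% and both say stop. Early deaths and progressions are also known failures, some diagnosable from blood under section 7.0, so fewer patients are truly pending than short follow-up suggests. That reduces how often rule and caption disagree. It does not change the literal stop probabilities, which depend only on when CRs become known.

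**Conclusion.** The point holds as an inconsistency between the Table 1a caption and the posterior rule it implements. Under the literal caption, any delay in documenting CR raises the stop probability at true CR 20% above 0.086. That direction needs no timing assumption. The exact values by number pending are those in the working.

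The size in practice is not determined by the documents. About 0.10 to 0.69 covers 2 to 5 patients per month, CR known from day 21 to uniformly over months 1–4, even or Poisson accrual, and crossings treated as final. Tables 1a, 1b and 4 agree with the posterior rule when all outcomes are known. What is missing is a correct denominator and a stated handling of pending patients. This should be fixed; it does not show that the design is unsound.

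**What to change.** Change the Table 1a denominator from patients accrued to patients whose CR outcome is determined, and give responders and non-responders the same entry rule so that neither enters earlier. Counting every patient on completing the 4-month window is the simplest unbiased form; another form is acceptable if it meets the same condition and its operating characteristics are shown. Responders should not enter on declaration while non-responders wait 4 months, because that lowers futility stopping well below Table 1b. State when the window starts, and restate Tables 1b and 4 for the chosen rule with the planned accrual and response delay.

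The drafting cost is a sentence or two and a rerun of the tables. The real cost is slower futility stopping. With even accrual and the completed-window form, 15 completed windows correspond to 15 + 4 × 2 = 23, 15 + 4 × 3.5 = 29 or 15 + 4 × 5 = 35 patients enrolled. Simulated with the window assumed to start on day 1 of cycle 1:

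| True CR | Instant outcomes | 2/month | 3.5/month | 5/month |
|---|---|---|---|---|
| 10%: P(stop) | 0.735 (stated) | 0.69–0.70 | 0.65–0.67 | 0.61–0.62 |
| 10%: mean N | 48 | 53 | 57 | 61 |
| 5%: P(stop) | 0.992 (stated) | 0.98–0.99 | 0.97–0.98 | 0.95–0.96 |
| 5%: mean N | 26 | 34 | 40 | 46 |
| 20%: P(stop) | 0.086 (stated) | 0.08 | 0.08 | 0.08 |

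In a population with a stated median survival below 6 months, the extra enrolment on an inactive regimen is a real price. The sponsor should weigh it when choosing the entry rule.

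### The overall-survival stopping rule as written stops about 19% to 24% of trials at the postulated 6-month median, not the 7.9% given in Table 2

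*Combined protocol and SAP*

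**What the plan says.** All of this is in section 10.0, Data Monitoring Plan.

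- **Model.** Survival times under the study and historical treatments "follow an exponential distribution with median Me and Ms , respectively". The study median Me has prior IG(3,12), with mean 6 and variance 36. For the historical treatment, "the prior for Ms follows Inverse Gamma (IG) (35, 204) to reflect our knowledge of overall survival from the historical data"; this prior has mean 6 and variance 1.09.
- **Rule.** The first look comes at 14 enrolled patients and looks then repeat monthly. "Formally, we'll stop the study early if there is < 5% chance that the median OS is 6 months or more". The reference is a fixed 6 months, and Ms does not appear in the rule.
- **Claimed performance.** "The operating characteristics of this decision rule are shown in the following table". That is Table 2, "Operating characteristics of Efficacy Monitoring(PL=0.05)", with stopping probabilities 1, 0.835, 0.079 and 0.024 at true medians of 2, 4, 6 and 7 months.
- **Accrual.** "A maximum of 80 patient will be accrued at a rate of 2 to 5 patients per month". The rate assumed for Table 2 is not given.
- **Carry-forward.** Table 4, "Operating characteristics considering efficacy and toxicity jointly", combines the stopping probabilities for CR, OS and toxicity under independence.
- **Conduct.** Under Trial Conduct, "The monitoring rules for the overall survival will be automatically evaluated each time patient data are updated on the trial website". This is a different look schedule from the monthly one.

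**The concern.** Two features suggest that the rule and the table do not belong together. First, an informative prior for the historical median is set out in detail and then has no role in the rule. Second, a 5% posterior cutoff applied monthly to accumulating data, with 6 months as both the prior mean and the threshold, should stop well over 5% of trials when the true median is 6 months. A cumulative 7.9% looks too low.

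OS is a primary endpoint and this rule alone can end the trial. Six months is also the median the plan postulates for the treatment, so 0.079 is the plan's stated chance of stopping a regimen that performs as postulated. If the written rule is the one applied, those who approved the plan relied on an error rate that does not describe it.

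**Working it through.** **Inputs (section 10.0).** Exponential survival; Me ~ IG(3,12); first look at the 14th enrolment, then monthly; maximum 80 patients; 2 to 5 per month; cutoff 0.05. Assumptions: Poisson accrual, no dropout, looks ending at the 80th enrolment.

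**Priors.** IG(a,b) has mean b/(a−1) and variance b²/[(a−1)²(a−2)].
- IG(3,12): mean 12/2 = 6, variance 144/(4×1) = 36.
- IG(35,204): mean 204/34 = 6, variance 36/33 = 1.09.

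Both agree with the plan.

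**Posterior.** With d deaths and total follow-up T person-months, Me | data ~ IG(3 + d, 12 + ln2 × T). The written rule stops when Pr(Me > 6 | data) < 0.05.

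**Worked example at 20 deaths.** The posterior shape is 23, and the 5% quantile of a Gamma(23,1) variable is 15.72. The rule stops when (12 + ln2 × T)/6 < 15.72. That is T < (94.32 − 12)/0.6931 = 118.8 person-months, a crude median of 0.6931 × 118.8/20 = 4.12 months. Comparing Me with Ms at the same cutoff stops only below T = 105.1 (crude median 3.64). The two rules therefore make different decisions.

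**Simulation of the written rule** (10,000 trials per cell, monthly looks):

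| True median (months) | Table 2: P(stop), mean N | 2 per month | 5 per month |
|---|---|---|---|
| 4 | 0.835, 42 | 0.981, 28.7 | 0.934, 39.2 |
| 6 | 0.079, 76 | 0.237, 68.3 | 0.194, 71.5 |
| 7 | 0.024, 79 | 0.074, 75.8 | 0.072, 76.3 |

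At 3 and 4 per month the 6-month row is 0.223 and 0.217 (4,000 trials each). Monte Carlo error at 6 months is below 0.01. At a 2-month median the rule always stops, as Table 2 says.

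**Plausibility.** A single look at the end of accrual already stops 0.057 to 0.059 of trials at a 6-month median. From patient 14 to patient 80 there are about 66/5 + 1 ≈ 14 to 66/2 + 1 = 34 monthly looks. A cumulative 0.079 over that many looks is not credible.

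**Other look schedules, 6-month median.**
- Weekly looks: 0.235 to 0.256.
- Every 2 months: about 0.17 to 0.22.
- Every 3 months: 0.15 to 0.20.
- Every 6 months: 0.11 to 0.17.
- Fixed instead of random spacing of arrivals: about 0.20 to 0.24.

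Only the single end-of-accrual look falls below 0.079. It contradicts the monthly schedule and Table 2's mean sample sizes.

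**Possible sources of Table 2.**
- Pr(Me > Ms | data) < 0.05 at 2/3/4/5 per month gives 0.840/0.812/0.769/0.732 at 4 months (mean N 39.5/43.0/46.5/49.5), 0.089/0.089/0.082/0.082 at 6, and 0.032 to 0.036 at 7. This is much closer, but no single rate fits every row: the 4-month row needs about 2 to 3 per month, while the mean of 18 patients at 2 months needs about 5.
- A fixed 6-month rule with cutoff 0.02 at 5 per month gives 0.844/0.085/0.023 at 4/6/7 months. It is about as close on P(stop), but mean N at 4 months is 48.9 against 42.

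**Table 4.** The printed rows follow from 1 − (1 − CR)(1 − OS)(1 − toxicity), using the stopping probabilities in Tables 1b, 2 and 3. For example, 1 − 0.914 × 0.921 × 0.812 = 0.316 and 1 − 0.265 × 0.921 × 0.988 = 0.759. Substituting the rounded ranges above (0.93–0.98, 0.19–0.24, 0.07–0.08):

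| CR, OS, toxicity | Printed | Written rule |
|---|---|---|
| 0.2, 6, 0.3 | 0.316 | 0.40–0.44 |
| 0.1, 6, 0.2 | 0.759 | 0.79–0.80 |
| 0.25, 4, 0.2 | 0.84 | 0.93–0.98 |
| 0.25, 7, 0.2 | 0.06 | 0.10–0.11 |
| 0.1, 4, 0.4 | 0.989 | 0.995–0.999 |
| 0.1, 7, 0.4 | 0.937 | 0.940 |
| 0.25, 7, 0.5 | 0.99 | 0.991 |

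Table 1b has no row for CR 0.25. The value used, 0.0233, was computed exactly from the Table 1a boundaries. The same calculation gives 0.086 at CR 0.2 and 0.739 at CR 0.1, against 0.086 and 0.735 in Table 1b.

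**The case against.** The strongest reply is that Table 2 may be sound and the sentence merely incomplete. The section sets up Me and Ms side by side, and the informative historical prior makes sense only if the two are compared, with 6 months as shorthand for a historical median of mean 6. On that reading the stopping probability at 6 months is 0.08 to 0.09, close to the table, and the extra stopping calculated here never occurs. This is plausible but unproven: no single accrual rate reproduces every row, and a different cutoff on the fixed rule fits about as well. It also does not remove the fault, because the formal rule still says something else.

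Several narrower points stand:

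- The extra stopping happens only if the website runs the written rule.
- Six months is also the historical mean, so stopping there does not discard a regimen better than history. At 7 months the absolute change is only about 0.05.
- At 4 months the written rule stops more often and exposes fewer patients.
- Three of the seven Table 4 rows barely move.
- Evaluation at each data update can coexist with a monthly minimum, and weekly looks add only about 0.02 to 0.04 at 6 months.
- The final Kaplan-Meier analysis is unaffected.

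These points limit the consequences but leave the mismatch in place.

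**Conclusion.** The concern holds and must be fixed. The plan cannot have both the stated OS rule and the stated error rates. Under the written rule the chance of stopping at the postulated 6-month median is 0.19 to 0.24, about 2.4 to 3 times the 0.079 in Table 2 (0.19/0.079 = 2.4; 0.24/0.079 = 3.0).

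This rests on exponential survival, the stated IG(3,12) prior, no dropout, and accrual anywhere in the planned 2 to 5 per month. Confidence in the mismatch is high. Which of the sentence and the table reflects the intended rule, and which rule the website applies, cannot be settled from the documents.

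**What to change.** 1. Confirm which OS rule the conduct website applies (fixed 6 months, or Me against Ms), with its cutoff and look schedule.
2. State exactly that rule in section 10.0, and reconcile monthly looks with evaluation at every data update.
3. Rerun Table 2 and the OS-dependent rows of Table 4 for that rule, stating the accrual rate and look schedule assumed.
4. If the fixed 6-month rule is intended, say that the Ms prior is not used in it.

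The cost is a sentence or two of text, a simulation rerun and restated tables, with no added patients. If the fixed rule is kept at its present cutoff, the plan must accept and report a stopping probability of about 0.2 at its own postulated median, alongside more frequent stopping at 4 months.
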